#### IRB: 9. Risk to Participants

List the reasonably foreseeable risks, discomforts, or inconveniences related to participation in the research.

#### TIPS for streamlining the review time.

- Consider the broad definition of "minimal risk" as the probability and magnitude of harm or discomfort anticipated in the research that are not greater in and of themselves than those ordinarily encountered in daily life or during the performance of routine physical or psychological examinations or tests.
- ✓ Consider physical, psychological, social, legal, and economic risks.

✓ If there are risks, clearly describe the plan for mitigating the identified risks.

#### Response:

There are no risks beyond regular physical activity participation. The after school program has had physical activity included in it so there are no additional risks with this program.

#### **IRB: 10. Potential Direct Benefits to Participants**

List the potential direct benefits to research participants. If there are risks noted in 9 (above), articulated benefits should outweigh such risks. These benefits are not to society or others not considered participants in the proposed research. Indicate if there is no direct benefit. A direct benefit comes as a direct result of the subject's participation in the research. An indirect benefit may be incidental to the subject's participation. Do not include compensation as a benefit.

Response:

Direct benefits include environmental upgrades to the playground facilities. Healthy school personnel and students will receive training in promoting social emotional learning through physical activity. Students will participate in the xxx curriculum with opportunities to develop their own social and emotional learning. Findings from this project will also be presented and published increasing the body of knowledge on our understanding of promoting social and emotional learning through physical activity.

# IRB: 11. Privacy and Confidentiality

Indicate the steps that will be taken to protect the participant's privacy.

- 11.1 Identify who will have access to the data.
- 11.2 Identify where, how, and how long data will be stored (e.g. ASU secure server, ASU cloud storage, filing cabinets).
- 11.3 Describe the procedures for sharing, managing and destroying data.

11.4 Describe any special measures to **protect** any extremely sensitive data (e.g. password protection, encryption, certificates of confidentiality, separation of identifiers and data, secured storage, etc.).

11.5 Describe how any audio or video recordings will be managed, secured, and/or de-identified.
Only participants with picture/video permission will be photographed or digitally video recorded.
11.6 Describe how will any signed consent, assent, and/or parental permission forms be secured and how long they will be maintained. These forms should separate from the rest of the study data.
11.7 Describe how any data will be de-identified, linked or tracked (e.g. master-list, contact list, reproducible participant ID, randomized ID, etc.). Outline the specific procedures and processes that will be followed.

11.8 Describe any and all identifying or contact information that will be collected for any reason during the course of the study and how it will be secured or protected. This includes contact information collected for follow-up, compensation, linking data, or recruitment.

11.9 For studies accessing existing data sets, clearly describe whether or not the data requires a Data Use Agreement or any other contracts/agreements to access it for research purposes. 11.10 For any data that may be covered under FERPA (student grades, etc.) additional information and requirements is available at

https://researchintegrity.asu.edu/human-subjects/special-considerations.

Response:

11.1 Data will be accessible only to members of the research team. All data will be de-identified prior to storage. Only unique student IDs will be accessible. School level data will be saved using students' ID as well (i.e., attendance, behavioral referrals, demographics).

11.2 Data will be stored in a locked file cabinet in the PI's locked office. Data from accelerometry will be stored on a password protected computer accessible only to the research team.

11.3 Data will be shared using only password protected files and will be destroyed five years after collection.

- 11.4 No identifying information will be stored, so extra protection for highly sensitive material is not warranted.
- 11.5 We will not obtain any audio or video recordings.
- 11.6 Consent and assent forms will be secured in a manilla envelope in a locked file cabinet in a locked room. They will be kept for 5 years. These forms will be kept separate from the rest of the data from the study.

11.7 We will use a master list of student IDs that will not be tied to any identifiable information. Any identifiable information included in this master list will be destroyed (deleted or shredded) as soon as the data are linked. These IDs will be used to link accelerometer devices to individual demographics such as sex and school.

11.8 No identifying information will be included in the research.

11.9 No secondary data will be utilized in this research.

11.10 We will not include any data covered under FERPA.

# IRB: 12. Consent

Describe the procedures that will be used to obtain consent or assent (and/or parental permission).

- 12.1 Who will be responsible for consenting participants?
- 12.2 Where will the consent process take place?
- 12.3 How will the consent be obtained (e.g., verbal, digital signature)?

#### TIPS for streamlining the review time.

- ✓ If participants who do not speak English will be enrolled, describe the process to ensure that the oral and/or written information provided to those participants will be in their preferred language. Indicate the language that will be used by those obtaining consent. For translation requirements, see Translating documents and materials under https://researchintegrity.asu.edu/human-subjects/protocol-submission
- Translated consent forms should be submitted after the English is version of all relevant materials are approved. Alternatively, submit translation certification letter.
- If a waiver for the informed consent process is requested, justify the waiver in terms of each of the following: (a) The research involves no more than minimal risk to the subjects; (b) The waiver or alteration will not adversely affect the rights and welfare of the subjects; (c) The research could not practicably be carried out without the waiver or alteration; and (d) Whenever appropriate, the subjects will be provided with additional pertinent information after participation. Studies involving confidential, one time, or anonymous data need not justify a waiver. A verbal consent or implied consent after reading a cover letter is sufficient.
- ✓ ASU consent templates are [here].
- ✓ Consents and related materials need to be congruent with the content of the application.

#### Response:

- 12.1 Members of the research team will be responsible for consent.
- 12.2 Consenting will take place in person at the school site and through electronic communication. Initially, we will ask principals at 14 participating schools to provide informed consent, share their school bell schedule, and assist with recruiting all healthy school personnel in their school to participate. After-school program leaders will be asked to send this information to all parents/guardians. Those interested in enrolling their child will return the signed consent/e-consent (ESSER parent permission\_06.29.22). Child assent will be obtained for students in grades 3-6.
- 12.3 Written documentation of consent will be obtained for adults, and written assent will be collected for children and marked as obtained by researchers.

#### IRB: 13. Site(s) or locations where research will be conducted.

List the sites or locations where interactions with participants will occur-

- Identify where research procedures will be performed.
  - For research conducted outside of the ASU describe:
    - o Site-specific regulations or customs affecting the research.
    - o Local scientific and ethical review structures in place.
  - For research conducted outside of the United States/United States Territories describe:
    - Safeguards to ensure participants are protected.
    - For information on international research, review the content xxx
- For research conducted with secondary data (archived data):
  - List what data will be collected and from where.
  - Describe whether or not the data requires a Data Use Agreement or any other
  - contracts/agreements to access it for research purposes.
  - For any data that may be covered under FERPA (student grades, etc.) additional information and requirements is available xxx
  - For any data that may be covered under FERPA (student grades, homework assignments, student ID numbers etc.), additional information and requirements is available xxx

## Response:

Research will be conducted at 14 xxx Schools that have after-school programs. Data will be collected during the after school program and during recess. Accelerometers will be worn for 24 hours across seven days.

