#### Response:

We are using a crossover pre/post study design where seven after-school programs would receive the intervention in years 1 and 2 and seven schools would serve as matched comparison sites. During year two, the next seven schools would receive the intervention. This tiered approach begins with an initial assessment of the playgrounds to ensure that designs include the research-based elements of balancing, brachiating, climbing, spinning, sliding, and swinging. During years 1 & 2, Healthy School Staff will be trained with the xxx curriculum and the children will be trained as Peer Leaders (Fall Semesters 2022 and 2023) who are enrolled in the after-school program who then become peer leaders for all children during recess at their school.

Assessments include Physical, Social and Emotional Health Assessments administered fall and spring semesters of both years to track student behaviors. Assessments of the after-school setting will be conducted by Xplore program leaders on paper and include observations of all students attending Xplore programs. Assessments during recess would be conducted by recess aides/healthy school staff and would include a random sample of 25 students at recess. No identifying information will be recorded. Assessments will take approximately 5-10 minutes to complete. A copy of the assessment is included (K-6 Assessment).

We will ask the Healthy School Staff to complete a survey each fall and spring semester to learn about their perceptions of the training and playground activities. The survey will take approximately 5-10 minutes to complete. A copy of the staff assessment is included (Healthy School Staff Survey). Healthy School Staff may also be asked to participate in a 30-minute interview each spring semester.

We will ask students to complete a short survey about their physical, social, and emotional health and perceptions of the play activities in the program twice a year. The survey will take approximately 5-10 minutes to complete. A copy of the student assessment is included (Student Survey).

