We will also track student participants' physical activity patterns each semester via accelerometry (total of 4 times) for the 7 intervention schools student participants (n=147), and at the other 7 program schools during their control condition year (n=147). Students will wear ActiGraph GT3X+ accelerometer devices for 24 hours over a period of seven days twice a year. Three members of our research team will visit the after school program to set up the students with devices, and on the following week to collect the devices. Students will initially be shown how to secure the devices using the easy velcro wristband upon arrival at the program in the afternoon by the research team. Participants will wear accelerometers on their wrist to promote greater wear compliance compared to the hip among children. The match-box sized accelerometers are the most commonly used accelerometers in PA research and have been utilized by our research team in studies involving elementary schoolchildren. If a participant loses the accelerometer, they will be asked to immediately inform the front office staff who will inform our research team via email. Each child participant will be assigned a unique unidentifiable number (study ID) which will be linked to a person and used throughout the study.

Students may also be asked to participate in a small group interview for 15 minutes about the changes in their afterschool program at the end of each semester.

The research team will collect attendance, behavioral referral information at the school level without names. As well as demographic information for student participants only (gender, age, race/ethnicity) at all schools from the front office staff at the end of each semester to look for significant relationships between participation in the project and reduced behavior referrals as well as increase attendance. The school district personnel have agreed to the study design and measures. This data will only be collected for participants in this project.

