A cluster randomized controlled trial of an after-school playground curriculum intervention to improve children's physical, social, and emotional health: Study protocol for the PLAYground project

NCT ID not yet assigned

Date: June 20, 2022

Statistical Analysis Plan

Data analysis

Intervention effects on the primary trial outcomes (at each follow-up time point) will be assessed using general linear mixed effects models to account for the clustering of individual measurements within schools. These will include fixed effects for treatment group (intervention vs control), time (baseline and follow-up), and interaction term (intervention x time); include school as a random effect; and be adjusted for covariates related to the outcome (eg, student sex, age). Analyses related to physical, social, and emotional health will be performed with the child (nested within a school) as the unit of analysis. Analysis related to attendance and behavioral change will be performed with the school as the level of analysis. Separate analyses will be performed at each follow-up time point. Schools will be included in analyses if they meet at least 80% adherence to the protocol.

Secondary implementation outcomes will be assessed using descriptive statistics for Healthy Staff and Student survey data (appropriateness and feasibility) and data from monthly observations (fidelity and sustainability). Frequencies, means, and standard deviations will be calculated to describe the distributions, measures of central tendency, and dispersion of item responses. Data from Healthy Staff and Student interviews will be analyzed using a matrix analysis to summarize and organize data in alignment with Proctor's dimensions (adherence, exposure/dose, quality of delivery, component differentiation, and participant involvement), and content analysis to identify salient themes for each school, by school-level income, and collectively among intervention school groups. We will utilize a deductive approach, but allow for additional themes to emerge.

Sample size calculation

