The average enrollment of schools in the study district is 610 students. The average enrollment in all 14 after school programs across schools in the study district is 420 students. Using an estimate of a 70% participation rate among after-school programs and assuming 20% loss-to-follow-up, a sample of 7 intervention and 7 control schools will provide a sample of approximately 294 students (147 intervention and 147 control) at follow-up. Assuming an intra class correlation coefficient of 0.05 with 80% power and an alpha of 0.05, the sample will be sufficient to detect an effect size of .370, similar to other school-based PA interventions reporting small overall effects.

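### The plan states no way to measure an enrolled child who leaves the after-school program but stays at the school, so the spring accelerometer comparison (and probably the survey) can depend on who remains.

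*Protocol*

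**What the plan says.** The Protocol's procedures section (IRB: 7, Response) gives one route for accelerometry: "Three members of our research team will visit the after school program to set up the students with devices". The device is fitted "upon arrival at the program in the afternoon by the research team", and the team returns the following week to collect it. No other hand-out or collection point is described.

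The same section describes two observational assessments. The one led by program staff will "include observations of all students attending Xplore programs". The recess one "would include a random sample of 25 students at recess". Neither records identifying information. The student survey is given twice a year and has no setting of its own. The only general statement of setting is in IRB: 13: "Data will be collected during the after school program and during recess". Demographics, attendance and behavior referrals come from the front office.

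The SAP (Data analysis) analyses the physical, social and emotional outcomes with the child as the unit. It fits group, time and their interaction, adjusts for covariates such as sex and age, and will "include school as a random effect". No child-level effect is named. The sample size section gives a follow-up sample of 294, "assuming 20% loss-to-follow-up".

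Neither document says whether a child who leaves the program but remains at the school is still measured. Neither gives a missing-data method or an attrition sensitivity analysis.

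**The concern.** The after-school program is both where the intervention is delivered and where enrolled children are reached for measurement. The intervention changes what the program offers, so it may change which children are still there in spring. If it does, the children measured in spring have been selected after allocation, and selected differently in the two arms.

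Suppose, for example, that less active children tend to leave the more active programs. The spring mean in intervention schools would then rise without any child having changed. If very active children leave for other activities, the mean would fall. Recruiting more schools would not remove either effect.

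**Working it through.** **Step 1: which data sources can follow an enrolled child who has left the program?**
- Accelerometry: linked by study ID, but fitted and collected only at the program. Not reachable as written.
- Student survey: no stated setting beyond IRB: 13. Probably not reachable, by inference.
- Program-leader observation: covers whoever attends at the time and is unlinked. It does not follow individuals and can include later joiners.
- Recess observation: a random, anonymous sample. It cannot stand in for an enrolled child's follow-up.
- Front-office attendance and referrals: do not depend on staying in the program.

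The gap therefore concerns accelerometry, and the survey by inference.

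**Step 2: what does the stated model do with a missing spring value?** With school as the only random effect, a child's fall and spring values are treated as unrelated once school and covariates are allowed for. A leaver's fall value counts in the fall mean but carries no information about that child's spring value. The group-by-time term then compares all enrolled children in fall with those still reachable in spring. Covariates such as sex and age correct only the selection they explain.

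**Step 3: the plan's own figures.** From the SAP sample size section:
- 420 x 0.70 = 294, and 294 x 0.80 = 235.2. The stated 294 is the number before the 20% loss, although the SAP labels it as the follow-up number.
- Per school: 294/14 = 21 before loss and 235.2/14 = 16.8 after it.
- Detectable effect = (1.960 + 0.842) x sqrt(2 x DE/(7m)), with DE = 1 + (m - 1) x 0.05, assuming a two-sided test. At m = 21, DE = 2.00 and the result is 0.462. At m = 16.8, DE = 1.79 and the result is 0.489. The stated .370 is not reproduced. That is a separate matter, but it affects what the bias should be compared with.

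**Step 4: precision.** The variance of a school mean is proportional to DE/m.
- m = 21: 2.00/21 = 0.0952.
- m = 16.8: 1.79/16.8 = 0.1065.
- Standard error ratio: sqrt(0.1065/0.0952) = 1.06.

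Losing the full 20% costs about 6% in standard error, so the issue is bias and not precision.

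**Step 5: bias, by assumption.** Let a fraction p of an arm leave, and let leavers differ from the mean of all enrolled children in that arm by d SD. The mean of those who stay moves by p x d/(1 - p) in the opposite direction. With equal p in both arms, the bias in the contrast is p/(1 - p) times the between-arm difference in d. Assume all of the planned 20% is program leaving, so p/(1 - p) = 0.20/0.80 = 0.25.

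| Difference in d between arms (SD) | Shift (SD) | Share of .370 | Share of 0.462 |
|---|---|---|---|
| 0 | 0 | 0% | 0% |
| 0.3 | 0.075 | 20% | 16% |
| 0.5 | 0.125 | 34% | 27% |
| 0.8 | 0.20 | 54% | 43% |

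The sign can go either way.

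Retention may also differ by arm while the stayer-minus-leaver gap g is common to both. The bias is then g times the difference in the fractions leaving:
- Retention 85% v 75%: 0.10 x 0.25 = 0.025 SD to 0.10 x 0.5 = 0.05 SD.
- Retention 90% v 70%: 0.20 x 0.25 = 0.05 SD to 0.20 x 0.5 = 0.10 SD.

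Retention by arm, d and g are not in the documents.

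**The case against.** The strongest reply is that the plan is silent on leavers and does not exclude them. A reader might infer that these children are certainly lost. The documents do not say so. The note under IRB: 8 has all participants taking part in both years, which describes a continuing cohort. IRB: 13 also names recess, where a survey could be given. Lost devices are reported through the front office, so a school-day contact route exists. What stands is narrower: no procedure for measuring leavers is stated, and the one device route that is stated would miss them.

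A reader might also infer that most of the 20% loss is avoidable. The SAP gives no cause for it. It could be school moves, absence, withdrawal or devices not worn, and the shifts shown shrink in proportion if only part of it is program leaving.

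A third reply is that selection on a child's starting level can largely be handled in the analysis, through a child-level random effect or baseline adjustment, with no extra fieldwork. That is right, and it belongs in the fix. It does not deal with selection on change, where leavers would have responded differently from children with similar fall values. Only measuring them addresses that.

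Finally, reaching leavers is not free. The team currently visits in the afternoon. Separate school-day contacts to fit and to collect devices could number up to 2 x 14 = 28 per wave, and district personnel agreed to the existing design.

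**Conclusion.** The point holds for accelerometry and, by inference, for the student survey. Followed as written, the plan has no way to measure an enrolled child who leaves the program but stays at the school, and the stated model makes no use of that child's fall value in spring. It does not apply to the unlinked program-leader observations, whose spring group is whoever attends, or to the front-office attendance and referral data.

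A reader might go further and infer that the trial will overstate the effect. The documents do not support that. They give neither retention by arm nor any description of who leaves, so both size and direction are unknown, and equal loss of similar children would give no bias. The range of 0.075 to 0.20 SD rests on assuming that all of the 20% is program leaving and that the leavers' gap differs by 0.3 to 0.8 SD between arms. It shows that a plausible imbalance would not be negligible beside the effect the trial hopes to detect. The change is worth making because a wave of measurement that is missed cannot be recovered later.

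**What to change.** - **Protocol, IRB: 7 and IRB: 13.** State that every enrolled child still attending the school is offered the device and the survey at each wave, whether or not still in the program. Provide school-day hand-out and collection for those who have left; the bell schedules requested from principals under IRB: 12 would help with timing.
- **Definition of loss.** Count as lost only children who left the school, withdrew or gave no valid data. Report loss by arm and reason.
- **SAP, Data analysis.** Analyse all enrolled children by their school's assigned condition, regardless of program attendance. Add a child-level random effect or baseline adjustment so that a leaver's fall value is used.

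If the team already intends to follow leavers, the protocol part needs only a sentence or two. Otherwise the cost is a few extra contacts: if the whole 20% were program leaving, about 0.20 x 21 = 4 children per school per wave, each needing a device fitted and collected. The number may grow over the waves, and school-day access may need district agreement. The estimated effect may be slightly smaller, because children who stopped attending are included.
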